#### **4.4. End of Study Definition**

##### **End of Study Definition**

The end of study is considered as the last visit for the last participant in the study. The final data from the study site will be sent to the sponsor (or designee) after completion of the final participant visit at that study site, in the time frame specified in the clinical trial agreement.

##### **Study Completion Definition**

A participant will be considered to have completed the study if the participant has completed all assessments at the follow-up visit (ie, Week 20).

### **5. STUDY POPULATION**

Screening for eligible participants will be performed within 4 weeks before administration of the study intervention. Refer to Section 5.4., Screen Failures for conditions under which the repeat of any screening procedures are allowed.

The inclusion and exclusion criteria for enrolling participants in this study are described below. If there is a question about these criteria, the investigator must consult with the appropriate sponsor representative and resolve any issues before enrolling a participant in the study. Waivers are not allowed.

For a discussion of the statistical considerations of participant selection, refer to Section 9.2 Sample Size Determination.

#### **5.1. Inclusion Criteria**

Each potential participant must satisfy all of the following criteria to be enrolled in the study:

##### **Age**

1. 18 (or the legal age of consent in the jurisdiction in which the study is taking place) to 75 years of age, inclusive.

##### **Type of Participant and Disease Characteristics**

2. has a diagnosis of plaque psoriasis, with or without psoriatic arthritis, for at least 26 weeks prior to the first administration of study intervention.

3. has a total BSA  $\geq 10\%$  at screening and baseline.
4. has a total PASI  $\geq 12$  at screening and baseline.
5. has a total IGA  $\geq 3$  at screening and baseline.
6. be a candidate for phototherapy or systemic treatment for plaque psoriasis.
7. must agree to avoid prolonged sun exposure and avoid use of tanning booths or other ultraviolet (UV) light sources during the study.
8. otherwise healthy on the basis of physical examination, medical history, and vital signs, and 12-lead triplicate electrocardiogram (ECG) performed at screening. Any abnormalities must be consistent with the underlying illness in the study population and this determination must be recorded in the participant's source documents and initialed by the investigator.

**Weight**

9. body mass index (BMI)  $\leq 40$ .

**Sex and Contraceptive/Barrier Requirements**

10. a woman of childbearing potential must have a negative highly sensitive serum ( $\beta$ -human chorionic gonadotropin [ $\beta$ -hCG]) at screening and a negative urine pregnancy test at Week 0 prior to administration of study intervention.
11. a woman must be (as defined in Section 10.5, Appendix 5: Contraceptive and Barrier Guidance):
  - a. Not of childbearing potential
  - b. Of childbearing potential and
    - Practicing a highly effective method of contraception (failure rate of  $<1\%$  per year when used consistently and correctly) prior to receiving study intervention, during the study, and for at least 12 weeks after receiving the last administration of study intervention, consistent with local regulations regarding the use of birth control methods for participants participating in clinical studies. Examples of highly effective methods of contraception are in Section 10.5, Appendix 5: Contraceptive and Barrier Guidance.
    - The investigator should evaluate the potential for contraceptive method failure (eg, noncompliance, recently initiated) in relationship to the first administration of study intervention.

Note: If a female participant's childbearing potential changes after start of the study (eg, a woman who is not heterosexually active becomes active, a premenarchal woman experiences menarche), she must begin practicing a highly effective method of birth control, as described above.

12. a woman must agree not to donate eggs (ova, oocytes) or freeze for future use for the purposes of assisted reproduction during the study and for at least 12 weeks after receiving the last administration of study intervention.
13. a male participant who is sexually active with a woman of childbearing potential and who has not had a vasectomy must agree to use a barrier method of birth control (eg, either a condom [with spermicidal foam/gel/film/cream/suppository if available in their locale] or a partner with an occlusive cap [diaphragm or cervical/vault caps] plus spermicidal foam/gel/film/cream/suppository if available in their locale), during the study and for at least 12 weeks after receiving the last administration of study intervention. Male participants should also be advised of the benefit for female partner to use a highly effective method of contraceptive as condoms may break or leak.
14. a male participant must agree not to donate sperm for the purpose of reproduction during the study and for a minimum of 12 weeks after receiving the last administration of study intervention.

### **Informed Consent**

15. must sign an informed consent form (ICF) indicating that the participant understands the purpose of, and procedures required for, the study and is willing to participate in the study.
16. must sign a separate ICF if the participant agrees to provide optional biomarker samples for research (where local regulations permit). Refusal to give consent for the optional biomarker research samples does not exclude a participant from participation in the study.
17. willing and able to adhere to the lifestyle restrictions specified in this protocol (refer to Section 5.3, Lifestyle Considerations for details).

### **Screening Laboratory Test Parameters**

18. have screening laboratory test results within the following parameters. If one or more of the laboratory parameters is out of range, a single retest of laboratory values is permitted:
  - a. Hemoglobin  $\geq 10$  g/dL (SI:  $\geq 100$  g/L)
  - b. White blood cells  $\geq 3.5 \times 10^3/\mu\text{L}$  (SI:  $\geq 3.5$  GI/L)
  - c. Neutrophils  $\geq 1.5 \times 10^3/\mu\text{L}$  (SI:  $\geq 1.5$  GI/L)
  - d. Platelets  $\geq 100 \times 10^3/\mu\text{L}$  (SI:  $\geq 100$  GI/L)
  - e. Estimated glomerular filtration rate (eGFR)  $\geq 60$  mL/min/1.73 m^2

- f. Aspartate aminotransferase  $\leq 2 \times$  upper limit of normal (ULN)
- g. Alanine aminotransferase  $\leq 2 \times$  ULN
- h. Alkaline phosphatase  $\leq 2 \times$  ULN

### **Vaccination**

- 19. agree not to receive a live virus or live bacterial vaccination during the study, or within 4 weeks after the last administration of study intervention.

## **5.2. Exclusion Criteria**

Any potential participant who meets any of the following criteria will be excluded from participating in the study:

### **Medical Conditions**

- 1. has a nonplaque form of psoriasis (eg, erythrodermic, guttate, or pustular).
- 2. has current drug-induced psoriasis (eg, a new onset of psoriasis or an exacerbation of psoriasis from beta blockers, calcium channel blockers, or lithium).
- 3. has a current diagnosis or signs or symptoms of severe, progressive, or uncontrolled renal, liver, cardiac, vascular, pulmonary, GI, endocrine, neurologic, hematologic, rheumatologic, psychiatric, or metabolic disturbances.
- 4. has any condition that interferes with GI absorption (ie, celiac disease, gastrectomy, ileostomy/colostomy, and GI fistula).
- 5. has a current diagnosis or history of disease(s) associated with intestinal epithelial barrier dysfunction, (ie, Crohn's disease, ulcerative colitis, collagenous colitis, celiac disease, primary biliary cholangitis, primary sclerosing cholangitis, nonalcoholic fatty liver disease, nonalcoholic steatohepatitis, and chronic pancreatitis).
- 6. known allergies, hypersensitivity, or intolerance to JNJ-77242113 or its excipients (refer to the JNJ-77242113 IB).
- 7. has had major surgery within 8 weeks before screening, or will not have fully recovered from surgery, or has surgery planned during the time the participant is expected to participate in the study.

**Note:** Participants with planned surgical procedures to be conducted under local anesthesia may participate.

- 8. has a transplanted organ (with exception of a corneal transplant >12 weeks before the first administration of study intervention).

9. has suicidal ideation or suicidal behavior in the last 26 weeks that may be defined as a Columbia Suicide Severity Rating Scale (C-SSRS) rating at screening of: Suicidal Ideation with Intention to Act (“Ideation level 4”), Suicidal Ideation with Specific Plan and Intent (“Ideation level 5”), or suicidal behavior (actual suicide attempt, interrupted suicide attempt, aborted suicide attempt, or preparatory behaviors for making a suicide attempt), and is considered to be at risk by the investigator based on an evaluation by a mental health professional. In addition, participants with C-SSRS ratings of Wish to be Dead (“Ideation level 1”), Non-Specific Active Suicidal Thoughts (“Ideation level 2”), Active Suicidal Ideation with Any Methods (Not Plan) without Intent to Act (“Ideation level 3”) or non-suicidal self-injurious behavior who are determined to be at risk by the investigator may not be randomized.

### **Prior/Concomitant Therapy**

10. has previously received any other therapeutic agent directly targeted to IL-23 (including but not limited to guselkumab, tildrakizumab, or risankizumab).
11. has received any therapeutic agent directly targeted to IL-17, IL-17 receptor, or IL-12/23 (including but not limited to secukinumab, ixekizumab, brodalumab, or ustekinumab) or has received biologic therapy targeting TNF (including but not limited to adalimumab, infliximab, or etanercept) within 12 weeks or 5 half-lives, whichever is longer, of the first administration of study intervention.
12. has received agents that deplete B cells (including but not limited to rituximab or alemtuzumab) within 26 weeks of the first administration of study intervention.
13. has received natalizumab, belimumab, or agents that modulate T cells (including but not limited to abatacept or visilizumab) within 12 weeks or 5 half-lives, whichever is longer, of the first administration of study intervention.
14. has received JAK inhibitor therapy (including but not limited to TYK2 inhibitors) within 4 weeks of the first administration of study intervention.
15. has received PDE4 inhibitor therapy (including but not limited to apremilast) within 4 weeks of the first administration of study intervention.
16. has received any systemic immunosuppressants (including, but not limited to, methotrexate [MTX], sulfasalazine, azathioprine, cyclosporine, 6-thioguanine, mercaptopurine, mycophenolate mofetil, gold, or tacrolimus) within 4 weeks of the first administration of study intervention.
17. has received proton pump inhibitors (including but not limited to omeprazole, esomeprazole, lansoprazole, rabeprazole, pantoprazole, dexlansoprazole, or Zegerid) within 1 week of first administration of study intervention.

18. has received, or is expected to receive, any live virus or bacterial vaccination within 12 weeks before the first administration of study intervention. For exclusions related to the Bacillus Calmette-Guérin (BCG) vaccine, see exclusion criterion 19.
19. has received the BCG vaccine within 52 weeks of the first administration of study intervention.
20. has received phototherapy or any systemic medications that could affect psoriasis or the PASI or IGA evaluations (including but not limited to oral or injectable corticosteroids, acitretin, retinoids, 1,25-dihydroxy vitamin D3 and analogues, lithium, antimalarials, herbal treatments, or traditional Taiwanese, Korean, or Chinese medicines) within 4 weeks of the first administration of study intervention.
21. has received topical therapies that could affect psoriasis or the PASI or IGA evaluation (including but not limited to corticosteroids, tar, anthralin, calcipotriene, tazarotene, methoxsalen, pimecrolimus, tacrolimus, or traditional Taiwanese, Korean, or Chinese medicines) within 2 weeks of the first administration of study intervention.

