JNJ-77242113 is a 13 amino acid peptide that binds directly to the IL-23R subunit and prevents IL-23 p19 from engaging its receptor, inhibiting proximal IL-23R signaling and downstream

effector functions (eg, cytokine secretion). Because of this validated mechanism of action in the treatment of moderate-to-severe psoriasis patients, JNJ-77242113 has the potential to have similar efficacy and safety profiles to subcutaneously administered anti-IL23 biologics, but with the convenience of oral administration. Validation of this treatment pathway in an orally administered form would significantly increase the therapeutic options for those patients in need of advanced therapies who prefer oral to subcutaneously administered medications.

Inclusion CCI [REDACTED] in the formulation offers potential to improve the CCI [REDACTED] and deliver efficacy CCI [REDACTED]. The mode of action CCI [REDACTED].

This study, 77242113PSO2003, is a randomized, double-blinded, placebo-controlled study designed to evaluate the efficacy, safety, and tolerability of a JNJ-77242113 oral delayed released tablet formulation CCI [REDACTED] (JNJ-77242113 CCI [REDACTED]), in adults with moderate-to-severe psoriasis. This study will be conducted in parallel with the complementary study 77242113PSO2001, a Phase 2b randomized, double-blinded, dose-ranging, placebo-controlled study designed to evaluate the efficacy and safety of JNJ-77242113, formulated as an CCI [REDACTED] in adults with moderate-to-severe plaque psoriasis.

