### **Prior/Concurrent Clinical Study Experience**

22. has received an experimental antibody or biologic therapy within 12 weeks or 5 half-lives of the first administration of study intervention or received any other experimental therapy or new investigational agent within 4 weeks or 5 half-lives (whichever is longer) of the first study intervention administration or is currently enrolled in another study using an investigational agent, device, or procedure.

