## Prohibited Therapy

All experimental therapies or new investigational interventions (except for JNJ-77242113), including therapies for psoriasis or other conditions, must be discontinued prior to the first administration of study intervention per exclusion criteria (Section 5.2, Exclusion Criteria) and remain prohibited during the study. For guidance regarding the COVID-19 vaccine see Section 10.7, Appendix 7: Guidance on Study Conduct During the COVID-19 Pandemic.

Use of proton pump inhibitors (including but not limited to omeprazole, esomeprazole, lansoprazole, rabeprazole, pantoprazole, dexlansoprazole, or Zegerid) is prohibited during the study, per exclusion criterion 17 (Section 5.2, Exclusion Criteria).

If a prohibited therapy is administered during the study, the medical monitor should be notified, and the participant may be required to discontinue from the study treatment per medical monitor's discretion. If a prohibited therapy is initiated during the follow-up period, the participant should still complete his or her final study visit, and the medication should be recorded as a concomitant therapy.

The sponsor must be notified in advance (or as soon as possible thereafter) of any instances in which prohibited therapies are administered.

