## 5.7.2. Immunogenicity

### 5.7.2.1. Antibodies to JNJ-77242113

Immune response analyses will be based on the Immunogenicity Analysis Set.

The incidence and titers of antibodies to JNJ-77242113 will be summarized for all participants who receive at least 1 dose of JNJ-77242113 and have appropriate samples for detection of antibodies to JNJ-77242113 (ie, participants with at least 1 sample obtained after their first dose of JNJ-77242113).

The antibody to JNJ-77242113 status (positive at any time, negative) and titers will be summarized by treatment group for participants who receive a dose of JNJ-77242113 and have appropriate samples for detection of antibodies to JNJ-77242113 (ie, participants with at least 1 sample obtained after their first dose of JNJ-77242113).

Participants evaluable for immunogenicity are defined as having at least 1 dose of JNJ-77242113 and have at least 1 valid blood sample drawn for antibody detection. The antibodies to JNJ-

77242113 summary and analysis will be based on the observed data; therefore, no imputation of missing data will be performed.

The following analysis of antibodies to JNJ-77242113 will be performed by treatment group:

- Summary of incidence of antibody to JNJ-77242113 status
- Summary of neutralizing antibodies (NAb) to JNJ-77242113

A listing of participants who are positive for antibodies to JNJ-77242113 will be provided. The sample antibody status, the titer, and the neutralizing antibody status to JNJ-77242113 will be listed by visit. This listing will also provide information regarding dose administered, JNJ-77242113 plasma concentration, PASI score, PASI75 response status, and IGA 0/1 response status for all applicable visits. In addition, a list of antibodies to JNJ-77242113 status in participants who discontinued study agent early will be provided.

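### Exclusion criterion 10 sets no lasting bar on earlier JNJ-77242113, so people who have left the parallel PSO2001 study can enter after 4 weeks off drug, and the SAP has no rule for antibodies already present at baseline

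*Protocol*

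**What the plan says.** Criterion 10 (Protocol 5.2) permanently excludes a person who "has previously received any other therapeutic agent directly targeted to IL-23 (including but not limited to guselkumab, tildrakizumab, or risankizumab". On the study drug's target, Protocol 2.1 says: "JNJ-77242113 is a 13 amino acid peptide that binds directly to the IL-23R subunit".

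Criterion 22 excludes a person who "received any other experimental therapy or new investigational agent within 4 weeks or 5 half-lives (whichever is longer) of the first study intervention administration", or who "is currently enrolled in another study using an investigational agent, device, or procedure". Criterion 20 adds a 4-week washout for systemic medication that could affect psoriasis. Criterion 26 leaves other confounding conditions to the investigator. Criterion 6 concerns only known allergy or intolerance to the drug.

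Protocol 2.1 also says: "This study will be conducted in parallel with the complementary study 77242113PSO2001". That is a placebo-controlled Phase 2b study of the same compound in moderate-to-severe plaque psoriasis.

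On immunogenicity, SAP 5.7.2.1 summarizes by treatment group "The antibody to JNJ-77242113 status (positive at any time, negative"), with no separate category for participants who are positive before their first dose.

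**The concern.** The protocol treats past use of another IL-23 agent as a permanent reason for exclusion, yet past use of the study drug only as a 4-week washout. It gives no reason for the difference. PSO2001 makes the question practical, because it is a concurrent source of exposed people with the same disease.

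Two results could be affected. First, former PSO2001 participants who still or again meet PASI 12 or more may include people who did not respond to this mechanism. Enrolling them would dilute the active-versus-placebo difference in an 80-person proof-of-concept trial. Prior JNJ-77242113 is not a stratification factor (Protocol 6.3), a listed per-protocol criterion (SAP 4) or a listed subgroup (SAP 5.7.5), so the planned analyses would not show it. Second, antibodies formed in PSO2001 could be reported as incidence in this study. Antibody incidence is an exploratory endpoint, and the protocol's own risk table (2.3.1) links such antibodies to reduced efficacy and hypersensitivity.

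**Working it through.** **1. Does any criterion reach earlier JNJ-77242113?**

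| Criterion (Protocol 5.2) | Reaches earlier JNJ-77242113? |
|---|---|
| 6 | Only with known allergy, hypersensitivity or intolerance |
| 10 | No: limited to other agents, and names IL-23 but not its receptor |
| 11 | No: IL-17, IL-17 receptor, IL-12/23 and TNF only |
| 20 | Within 4 weeks |
| 22 | Within 4 weeks or 5 half-lives, or while still enrolled elsewhere |
| 26 | At the investigator's discretion |

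Criterion 11 names a receptor alongside its ligand; criterion 10 does not.

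**2. Length of the washout.** The half-life is 9 to 12 hours (Protocol 4.3). Five half-lives are 5 × 9 = 45 h to 5 × 12 = 60 h, or 1.9 to 2.5 days. The 4-week limb is longer and governs. Twenty-eight days (672 h) is 672/12 = 56 to 672/9 = 75 half-lives, so residual drug is negligible. Any efficacy effect would come from who is selected, or from a lasting pharmacodynamic effect.

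**3. The plan's own power.** Protocol 9.2 claims at least 90% power for a 35-point difference with 20 placebo and 30 active participants at two-sided 0.10. For the pooled Z-test:

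Power = Φ[(pA − pP − 1.645·s0)/s1], with s0 = √[p̄(1 − p̄)(1/20 + 1/30)], s1 = √[pP(1 − pP)/20 + pA(1 − pA)/30] and p̄ = (20pP + 30pA)/50.

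- 5% vs 40%: p̄ = 0.26, s0 = 0.1266, s1 = 0.1019; (0.35 − 0.2083)/0.1019 = 1.39, so 91.8%.
- 10% vs 45%: p̄ = 0.31, s0 = 0.1335, s1 = 0.1129; (0.35 − 0.2196)/0.1129 = 1.155, so 87.6%.

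The unpooled version gives 96.3% and 92.7%, and exact enumeration gives 94.8% and 90.2%. The plan's figure therefore reproduces at both ends with either of those.

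**4. Hypothetical dilution.** Assume a fraction f of participants is prior-exposed and responds at the placebo rate in every arm. The active rate becomes pA′ = (1 − f)·pA + f·pP and the placebo rate is unchanged. For 10% vs 45%, f = 10% gives 0.9 × 0.45 + 0.1 × 0.10 = 0.415, and f = 20% gives 0.38. Pooled Z-test power:

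| f | Exposed of 80 | 5% vs 40% | 10% vs 45% | 10% vs 60% | 10% vs 80% |
|---|---|---|---|---|---|
| 0 | 0 | 91.8% | 87.6% | 99.2% | >99.8% |
| 10% | 8 | 86.9% | 81.3% | 97.5% | >99.8% |
| 20% | 16 | 80.3% | 73.5% | 93.9% | >99.8% |

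With a single exposed participant among the 30 in an active arm, 10% vs 45% moves only from 87.6% to 85.7%. Neither f nor the response rate of exposed people comes from the documents.

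**5. Antibodies.** One carried-over positive adds 1/30 = 3.3 points to an active arm's reported incidence. The Schedule of Activities plans an antibody sample at Week 0, taken before dosing (footnote r), so such a participant could be identified. The SAP does not say how that sample is used.

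**The case against.** The strongest reply is that the route is narrow and its effect speculative. A person must leave PSO2001 entirely, be 4 weeks off drug, meet the BSA, PASI and IGA levels at both screening and baseline, and do so while a small parallel trial is still recruiting. Criterion 26 allows exclusion, and Protocol 5 requires eligibility questions to be settled with the sponsor before enrolment. PSO2001's sites, calendar and own rules are not in these documents. This stands: nothing shows that anyone would cross over.

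The placebo-level response assumption is also weak. A relapser responded once and may respond again. Former PSO2001 placebo participants are drug-naive. PSO2001 uses a different, immediate-release formulation, so failure there need not predict failure here. The 10% vs 45% case is an unfavourable corner of the 40% to 80% planning range. All of this stands, and it limits the power figures to illustrations.

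A reader might infer bias between arms. The documents do not support that: randomization balances prior exposure in expectation, so the effect would be dilution, with no inflation of false positives.

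A reader might also take the Prohibited Therapy wording in Protocol 6.8, "All experimental therapies or new investigational interventions (except for JNJ-77242113), including therapies for psoriasis or other conditions", as permission for earlier exposure. It is not. That sentence keeps experimental therapies prohibited during the study, and without the exception it would prohibit the study drug itself.

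Finally, if the peptide were classed as an experimental biologic, criterion 22 would require 12 weeks or 5 half-lives. That is still no lasting bar, and Protocol 6.1 types the product as a drug.

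The reply does not remove the eligibility gap or the missing rule for baseline-positive antibodies.

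**Conclusion.** The gap is in the text: no criterion permanently bars earlier JNJ-77242113, and the effective limit is 4 weeks off drug plus having left any other study. The consequence is a risk of unknown size, not a demonstrated contamination.

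If 10% of participants were prior-exposed and responded at the placebo rate, power would fall by 6.3 points (87.6% to 81.3%) at 10% vs 45% and by 1.7 points (99.2% to 97.5%) at 10% vs 60%. At 10% vs 80% the loss is negligible. These figures rest on an assumed crossover fraction and response rate.

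The antibody point depends on fewer assumptions: antibodies from earlier exposure would count under the SAP's status definition, at 3.3 points per participant in a 30-person arm, although the Week 0 sample would identify them. The change is worth making because it is cheap and removes an unexplained asymmetry with other IL-23 agents.

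**What to change.** Reword criterion 10 to exclude anyone who has previously received JNJ-77242113, or who was randomized in a JNJ-77242113 study and whose treatment is still blinded, or who has received any other agent directly targeted to IL-23 or the IL-23 receptor. The blinded-treatment clause avoids unblinding PSO2001 to settle eligibility.

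In SAP 5.7.2.1, report participants who are antibody-positive at Week 0 separately from treatment-emergent antibody incidence. The eligibility change alone does not supply this rule.

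If the sponsor intends to admit people with prior exposure, the protocol should say so and reconcile criteria 10 and 22 with that intention.

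The cost is one clause in the protocol, one rule in the SAP, and the loss of a few candidates, including some who received only placebo in PSO2001. The sample size, endpoints and tests do not change.
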